2.2 Secondary objectives

The secondary objectives of this study are:

- To describe the time to reach maximum analyte concentration (t_{max}), time of last quantifiable analyte concentration (t_{last}), terminal rate constant (λ_z), and terminal half-life ($t_{1/2}$) of both dapagliflozin and metformin when administered as an IR FDC tablet and as individual tablet components in the fasted state in healthy volunteers.
- To describe the t_{max} , t_{last} , λ_z and $t_{1/2}$ of both dapagliflozin and metformin when administered as an IR FDC tablet and as individual tablet components in the fed state in healthy volunteers.
- To describe the effect of food on the PK profile (C_{max} , AUC, AUC_(0-t), t_{max} , t_{last} , λ_z and elimination $t_{1/2}$ of both dapagliflozin and metformin) of the dapagliflozin/metformin (5 mg/850 mg) IR FDC tablet compared to when administered in the fasted state in healthy volunteers.
- To assess the safety and tolerability of the dapagliflozin/metformin (5 mg/850 mg) IR FDC tablet and of 5-mg dapagliflozin and 850-mg Glucophage[®] (marketed in Canada by SA) administered together in the fasted and fed states in healthy volunteers.
- To demonstrate bioequivalence of a dapagliflozin/metformin (5 mg/850 mg) IR FDC tablet relative to 5-mg dapagliflozin and 850-mg Glucophage[®] (marketed in Canada by SA) tablets administered together in the fasted state in healthy volunteers with analysis performed using the nominal drug dose and corrected for the measured potency of the administered formulations.
- To demonstrate potency-corrected bioequivalence of a dapagliflozin/metformin (5 mg/850 mg) IR FDC tablet relative to 5-mg dapagliflozin and 850-mg Glucophage[®] (marketed in Canada by SA) tablets administered together in the fed

state in healthy volunteers with analysis performed using the nominal drug dose and corrected for the measured potency of the administered formulations.

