Visit window	≤28 days prior to randomisation	Day -1 to Day 4	7 to 10 days after last dose
Signed Informed Consent	X		
Inclusion/exclusion criteria	X	X ^a	
Concomitant medication	X	X	X
Medical /surgical history	X		
Physical examination	X	X ^b	X
Serology ^c	X		
Demographics	X		
Weight and height	X		
Urine drugs of abuse screen and alcohol breath test ^d	X	X	
12-lead ECG	X		X
Vital signs (blood pressure, heart rate)	X	X ^e	X
Clinical chemistry, haematology, urinalysis	X	X ^f	X
Coagulation	X		
Randomisation		X ^g	
PK blood sampling ^h		X	
Administration of investigational medicinal product (IMP)		X ⁱ	
Pregnancy test (urine) ^j	X	X ^k	X
Serum follicle stimulating hormone (FSH) ^l	X		
Adverse events		X ^m	X
Serious adverse events	X	X	X

ECG=electrocardiogram; PK=pharmacokinetics; IMP=investigational medicinal product; FSH=follicle stimulating hormone; HBsAg=hepatitis B surface antigen; HCV=hepatitis C virus; HIV=human immunodeficiency virus

^a Eligibility will be confirmed prior to each dosing.

^b Brief physical examination on Day -1 at Visits 2 to 5.

^c Hepatitis B surface antigen (HBsAg), hepatitis C virus (HCV) and human immunodeficiency virus (HIV) screening.

^d Drugs of abuse and alcohol test at screening and each admission to the clinical unit.

^e Once daily during the residential period, ie, Day -1 and Day 1 (predose) to Day 4.

^f On Day -1 at Visits 2 to 5.

Clinical Study Protocol
Drug Substance Dapagliflozin/metformin
Study Code D1691C00007
Edition Number 1
Date [REDACTED]

- ^g Predose Day 1 of treatment period 1 (Visit 2).
- ^h Pharmacokinetic blood samples will be collected at 0 (pre-dose), 0.25, 0.5, 1, 1.5, 2, 3, 4, 5, 6, 8, 10, 12, 16, 24, 30, 36, 42, 48, 54, 60 and 72 hours postdose.
- ⁱ Day 1 of each treatment period (Visits 2 to 5).
- ^j Female volunteers must have a confirmed negative urine pregnancy test at screening and on Day -1 of each treatment period (Visits 2 to 5) prior to dosing.
- ^k Day -1 of each treatment period (Visits 2 to 5).
- ^l Postmenopausal females only. The FSH levels must be in the laboratory-defined postmenopausal range.
- ^m From first dose in treatment period 1 (Visit 2).

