6.2.2 Follow-up procedures

A poststudy medical examination will be performed 7 to 10 days after the last dose. This will be similar to the one performed at screening and will include a complete physical examination, vital signs, recording of a 12-lead paper electrocardiogram (ECG), blood samples for clinical chemistry and haematology analyses, a urine sample for urinalysis, and AE and concomitant medication questioning.

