12. STATISTICAL METHODS AND SAMPLE SIZE DETERMINATION BY QUINTILES

12.1 Description of analysis sets

12.1.1 Safety analysis set

All healthy volunteers who received at least one dose of randomised IMP, and for whom any postdose data are available will be included in the safety population. Throughout the safety results sections, erroneously treated healthy volunteers (eg, those randomised to treatment A but actually given Treatment B) will be accounted for in the actual treatment group.

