12.2 Methods of statistical analyses

The statistical analyses will be performed by Quintiles Inc, [REDACTED] by using SAS, version 9.1 or later. Quintiles SOPs and Work Instructions will be used as the default methodology if not otherwise specified.

Data will be presented by treatment. Missing data will result in a reduced sample size for that parameter. No action will be taken to handle missing data.

A healthy volunteer who withdraws prior to the last planned observation in a study period will be included in the analyses up to the time of discontinuation.

Plasma concentrations and derived PK parameters will be reported to 3 significant figures; standard deviation will be reported to 4 significant figures and CVs will be presented to 1 decimal place. For all other data types, mean, median, minimum and maximum values will be reported to the same degree of precision as the raw data and the standard deviation will be reported to one further degree of precision. Percentage frequencies will generally be presented to the nearest integer. For derived data, rounding should be applied after calculations have been performed.

The primary objectives of this study are to demonstrate bioequivalence of a dapagliflozin/metformin (5 mg/850 mg) IR FDC tablet relative to 5-mg dapagliflozin and 850-mg Glucophage[®] (marketed in Canada by SA) tablets administered together in the fasted state and to demonstrate the bioequivalence of a dapagliflozin/metformin (5 mg/850 mg) IR FDC tablet relative to 5-mg dapagliflozin and 850-mg Glucophage[®] (marketed in Canada by SA) tablets administered together in the fed state. These analyses will be performed using the nominal drug dose and corrected for the measured potency of the administered formulations.

In the fasted condition, point estimates and 90% confidence intervals for C_{max} , $AUC_{(0-t)}$, and AUC will be calculated for the Treatment B to Treatment A ratios of geometric means of dapagliflozin and metformin using a linear mixed effect model. In the fed condition, point estimates and 90% confidence intervals for C_{max} , $AUC_{(0-t)}$, and AUC will be calculated for the Treatment D to Treatment C ratios of geometric means of dapagliflozin and metformin using a linear mixed effect model. These estimates will be constructed from the results of fitting the linear mixed effect models for log-transformed data with treatment sequence and period as

Clinical Study Protocol
Drug Substance Dapagliflozin/metformin

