Drug Substance Dapagliflozin/metformin
Study Code D1691C00007
Edition Number 1
Date [REDACTED]

Figures of arithmetic mean concentration-time data will be presented on linear and semi-logarithmic scales by treatment. Individual concentration-time data will be graphically presented on linear and semi-logarithmic scales, with the semi-log plot presenting the regression line from which λ_z was estimated. Graphical presentations of PK data may be added at the discretion of the PK scientist.

Frequency distributions of gender and race will be tabulated by treatment. Summary statistics for age, body weight, height, and BMI will be tabulated by treatment.

All recorded AEs will be listed and tabulated by system organ class, preferred term and formulation. Vital signs and clinical laboratory test results will be listed and summarized by formulation. Any significant physical examination findings, ECG results, and clinical laboratory results will be listed.

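### Section 12.2 sets the safety tables by formulation, which merges fasted with fed dosing and conflicts with the protocol's by-treatment rule and its safety objective

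*Protocol*

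**What the plan says.** The last paragraph of protocol Section 12.2 fixes the axis of the safety tables. For adverse events: "All recorded AEs will be listed and tabulated by system organ class, preferred term and formulation". For the measured safety variables: "Vital signs and clinical laboratory test results will be listed and summarized by formulation".

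Three other places point to a different axis:

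- Section 12.2 opens its presentation rules with "Data will be presented by treatment". Sections 3.1 and 5.5.2 define four treatments. A and B are given fasted, C and D fed; A and C are the separate tablets, B and D the fixed-dose combination (FDC).
- Section 12.1.1 says that wrongly treated volunteers "will be accounted for in the actual treatment group", and its example is a mix-up between Treatments A and B.
- The safety objective in Section 2.2 covers the FDC tablet and the separate tablets "administered together in the fasted and fed states in healthy volunteers".

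On timing, Table 1 places the in-period laboratory tests "on Day -1 at Visits 2 to 5". Section 6.2.2 adds "blood samples for clinical chemistry and haematology analyses, a urine sample for urinalysis" at follow-up, 7 to 10 days after the last dose. Vital signs are taken more often: "Once daily during the residential period, ie, Day -1 and Day 1 (predose) to Day 4".

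**The concern.** The protocol does not use *treatment* and *formulation* as synonyms. The potency-correction text and Table 3 in Section 12.2 use *formulation* for the test or reference product, with no reference to food. The paragraph just before the safety sentences tabulates demographics by treatment. A programmer who follows the safety sentences literally would therefore build two columns, FDC and separate tablets, each mixing fasted and fed dosing.

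What is at stake is how readable the tolerability results are. Section 1.3 reports that headache and gastrointestinal intolerance were the most common AEs in the previous FDC study, and that both parts of that study were run in the fed state. Fasted tolerability of the FDC is thus something the present study adds, and a pooled table would not display it.

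A smaller matter sits beside this. Every laboratory sample inside a treatment period precedes that period's dose, and the protocol does not say which treatment such a value belongs to. Changing the axis to treatment would not settle that by itself.

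**Working it through.** **1. Reproduce the laboratory count.** Screening 1 + Day -1 in each of 4 periods + follow-up 1 = 1 + 4 + 1 = 6. Table 2 gives 6 samples each for clinical chemistry and haematology, so the schedule is read correctly.

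**2. Effect of the axis on the tables.** Under the by-treatment rule there are four columns, A, B, C and D. Under product alone there are two, A + C and B + D. Each volunteer receives every treatment once, so the exposures per column are:

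| Volunteers completing | By treatment (4 columns) | By product only (2 columns) |
|---|---|---|
| 32 | 32 | 2 × 32 = 64 |
| 36 | 36 | 2 × 36 = 72 |
| 40 | 40 | 2 × 40 = 80 |

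With 32 completers, the per-exposure AE rate in a pooled column is (32 × fasted rate + 32 × fed rate) / 64, the plain average of the two. Any pair of rates with the same average gives the same entry, so the table says nothing about food state.

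**3. Where the laboratory samples fall.** A period of 5 days from Day -1 to Day 4 has no Day 0, so Day -1 is the day before dosing. For an interval of *w* days between doses, the Day -1 sample of the next period comes *w* − 1 days after the previous dose: 7 − 1 = 6, 14 − 1 = 13, 21 − 1 = 20 days.

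| Sample | Most recent dose before it | Lag |
|---|---|---|
| Screening; Visit 2 Day -1 | none | – |
| Visits 3, 4, 5 Day -1 | periods 1, 2, 3 | 6 to 20 days |
| Follow-up (Visit 6) | period 4 | 7 to 10 days |

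Two of the six samples precede all dosing. The other four each follow one of the four doses. None lies within the 72 hours after a dose.

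**4. Vital signs.** Day -1, Day 1 predose, and Days 2, 3 and 4 make 5 readings per period, of which 3 are postdose. The predose matter in step 3 is therefore a laboratory matter; only the food-state conflict in step 2 concerns the vital-sign tables.

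**The case against.** The strongest reply is that table layout belongs to the statistical analysis plan, that *formulation* is never defined for the safety tables, and that the general by-treatment rule already covers them. Part of this stands. A rule for assigning a predose crossover laboratory value, and a choice of baseline, are commonly left to the analysis plan, and their absence is not an error. The table axis is different: the protocol does not leave it open, but names one that disagrees with its own general rule in the same section.

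It is also fair to say that nothing is lost. All AEs are listed, Section 6.4.3 records the date and time each one started, and each treatment carries its food state. No formal fed-versus-fasted safety comparison is planned.

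A reader might go further and infer any of the following. The document does not support them.

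- *The safety objective cannot be answered.* The listings allow results by food state to be rebuilt; only the specified summary tables fail to show them.
- *Laboratory tests are only ever predose.* Step 3 shows four of six samples following a dose.
- *Laboratory values are attributed to a product not yet taken.* The protocol never says that a Day -1 value is filed under the coming dose.
- *The balance of the design would then hide any difference.* Suppose values were filed that way, with equal sequence sizes and all volunteers completing. In a Williams square the FDC-labelled Day -1 values would be 2/8 before any dose, 4/8 after the separate tablets and 2/8 after the FDC in the other food state, with the mirror image for the separate tablets. For lasting effects F (FDC) and R (separate tablets), the expected labelled difference is (0.25F + 0.50R) − (0.25R + 0.50F) = −0.25(F − R). That is shrunk to a quarter and reversed in sign, not cancelled. Nothing in the protocol shows that a laboratory effect would last 6 or more days after a single dose.

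**Conclusion.** The point holds as a minor internal conflict. Followed literally, Section 12.2 would produce safety tables with two product columns instead of four treatment columns, and those tables would not show safety by food state although the objective names both states. This rests on reading *formulation* as product alone, which is how Section 12.2 uses the word elsewhere. If the authors meant the four treatments, the wording is wrong but the intended tables are right, and the same correction applies.

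The laboratory timing supports only a caution: Day -1 values are not on-treatment values of the period in which they are drawn. It does not show that the protocol mislabels them. The bioequivalence analysis is unaffected under either reading.

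**What to change.** In the last paragraph of Section 12.2, replace *formulation* with *treatment (A, B, C, D)* for the AE, vital-sign and laboratory tables.

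Add one clarifying sentence, there or in the analysis plan: Day -1 laboratory results are predose for their own period and are not summarised as on-treatment values of that period; Day -1 results of Visits 3 to 5 and the follow-up results follow the dose of the preceding period.

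The cost is a wording change and the matching table shells. No new samples, visits or data items are needed, because treatment, visit and AE start time are already recorded.

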12.3 Determination of sample size

Dapagliflozin

Assume there is no difference between the bioavailabilities of dapagliflozin from the 5-mg dapagliflozin/850 mg metformin FDC tablet versus dapagliflozin from co-administration of a 5-mg dapagliflozin tablet and an 850-mg Glucophage (marketed in Canada by SA) tablet under both fasted and fed conditions,

From Study D1691C00002, C_{max} , $AUC_{(0-t)}$, and AUC are log normally distributed with intra-subject standard deviations of 0.286, 0.081, and 0.093 for $\log(C_{max})$, $\log[AUC_{(0-t)}]$, and $\log[AUC]$, respectively.

Using a 90% power and a 2-sided alpha of 5%, there will need to be 3 healthy volunteers per treatment sequence, 12 healthy volunteers total, to conclude bioequivalence with respect to $AUC_{(0-t)}$ and AUC.

Using a 95% power and a 2-sided alpha of 5%, there will need to be 3 healthy volunteers per treatment sequence, 12 healthy volunteers total, to conclude bioequivalence with respect to $AUC_{(0-t)}$ and AUC.

If there is a 5% difference between the treatments, using a 90% power and a 2-sided alpha of 5%, there will need to be 3 healthy volunteers per treatment sequence, 12 healthy volunteers total, to conclude bioequivalence with respect to $AUC_{(0-t)}$ and AUC.

Assuming there is no difference in the C_{max} between the 2 treatments, there will need to be 7 healthy volunteers per treatment sequence, 28 healthy volunteers total, to have a 95% probability of the measured C_{max} of the test to reference product to be between 80% and 125%.

Clinical Study Protocol
Drug Substance Dapagliflozin/metformin
Study Code D1691C00007
Edition Number 1
Date [REDACTED]

If there is a 5% difference between treatments for C_{\max} , there will need to be 8 healthy volunteers per treatment sequence, 32 healthy volunteers total, to have a 95% probability of the measured C_{\max} of the test to reference product to be between 80% and 125%.

Metformin

Assume there is no difference between the bioavailabilities of metformin from the 5 mg dapagliflozin/850 mg metformin FDC tablet versus dapagliflozin from coadministration of a 5-mg dapagliflozin tablet and an 850-mg Glucophage (marketed in Canada by SA) tablet under both fasted and fed conditions.

From saxagliptin Study CV181081, C_{\max} , $AUC_{(0-t)}$, and AUC are log normally distributed with intra-subject standard deviations of 0.220, 0.180, and 0.174 for $\log(C_{\max})$, $\log[AUC_{(0-t)}]$, and $\log[AUC]$, respectively.

Using a 90% power and a 2-sided alpha of 5%, there will need to be 5 healthy volunteers per treatment sequence, 20 healthy volunteers total, to conclude bioequivalence with respect to $AUC_{(0-t)}$ and AUC.

Using a 95% power and a 2-sided alpha of 5%, there will need to be 6 healthy volunteers per treatment sequence, 24 healthy volunteers total, to conclude bioequivalence with respect to $AUC_{(0-t)}$ and AUC.

If there is a 5% difference between the treatments, using a 90% power and a 2-sided alpha of 5%, there will need to be 6 healthy volunteers per treatment sequence, 24 healthy volunteers total, to conclude bioequivalence with respect to $AUC_{(0-t)}$ and AUC.

Assuming there is no difference in the C_{\max} between the two treatments, there will need to be 4 healthy volunteers per treatment sequence, 16 healthy volunteers total, to have a 95% probability of the measured C_{\max} of the test to reference product to be between 80% and 125%.

If there is a 5% difference between treatments for C_{\max} , there will need to be 5 healthy volunteers per treatment sequence, 20 healthy volunteers total, to have a 95% probability of the measured C_{\max} of the test to reference product to be between 80% and 125%.

At least 36 healthy volunteers will be enrolled to ensure that 32 healthy volunteers complete the study. A maximum of 40 healthy volunteers may be enrolled.

The sample size was selected to be consistent with the research hypothesis as described in Section 1.2.

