The analysis will be performed using the nominal drug dose and corrected for the measured potency of the administered formulations. Point estimates and 90% confidence intervals for C_{\max} , $AUC_{(0-t)}$, and AUC will be calculated for the Test to Reference ratios of geometric means of dapagliflozin and metformin using a linear mixed effect model. The reference and test treatments are defined as Treatments A and B, respectively, for comparisons within the fasted state, and as Treatments C and D, respectively, for comparisons within the fed state. These estimates will be constructed from the results of fitting the linear mixed effect models for log-transformed data with treatment sequence and period as fixed effects and subject within sequence as a random effect. Point estimates of the ratios and their confidence intervals will then be transformed back to original scale in order to give point estimates for the ratios of geometric means and their confidence intervals. As per guidelines from Health Canada, bioequivalence will be demonstrated if the 90% confidence interval of the ratio of geometric means of AUC and C_{\max} of the test to reference is within 80% to 125%.

Effect of food for the dapagliflozin/metformin (5 mg/850 mg) IR FDC tablet will be analysed with a similar model as described above.

TABLE OF CONTENTS

PAGE

TITLE PAGE	1
PROTOCOL SYNOPSIS	2
TABLE OF CONTENTS	6
LIST OF ABBREVIATIONS AND DEFINITION OF TERMS	10
1. INTRODUCTION	13
1.1 Background	13
1.2 Research hypotheses.....	13
1.3 Rationale for conducting this study	14
1.4 Benefit/risk and ethical assessment	15
2. STUDY OBJECTIVES	16
2.1 Primary objectives	16
2.2 Secondary objectives	16
3. STUDY PLAN AND PROCEDURES	17
3.1 Overall study design and flow chart	17
3.2 Rationale for study design, doses and control groups	21
4. SUBJECT SELECTION CRITERIA.....	21
4.1 Inclusion criteria.....	21
4.2 Exclusion criteria.....	22
5. STUDY CONDUCT	24
5.1 Restrictions during the study	24
5.2 Subject enrolment and randomisation.....	25
5.2.1 Procedures for randomisation	26
5.3 Procedures for handling subjects incorrectly enrolled or randomised.....	26
5.4 Blinding and procedures for unblinding the study	26
5.5 Treatments.....	26
5.5.1 Identity of investigational medicinal product(s)	26
5.5.2 Doses and treatment regimens	26
5.5.3 Additional study drug	27
5.5.4 Labelling	27
5.5.5 Storage	28

5.6	Concomitant and post-study treatment(s)	28
5.7	Treatment compliance	28
5.7.1	Accountability	29

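### The 95% Cmax probability that sets 32 completers in Section 12.3 is right under none of the protocol's Cmax rules: about 76–85% under the 90% CI rule, about 99% under the point-estimate rule

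*Protocol*

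**What the plan says.** Section 12.3 takes the dapagliflozin variability from an earlier study, with "intra-subject standard deviations of 0.286, 0.081, and 0.093" for log Cmax, log AUC(0-t) and log AUC. The metformin values are "intra-subject standard deviations of 0.220, 0.180, and 0.174" in the same order.

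For dapagliflozin Cmax at no difference, "there will need to be 7 healthy volunteers per treatment sequence, 28 healthy volunteers total, to have a 95% probability of the measured" ratio lying between 80% and 125%. At a 5% difference, "there will need to be 8 healthy volunteers per treatment sequence, 32 healthy volunteers total, to have a 95% probability of the measured" ratio lying in the same range. The metformin Cmax figures are 16 at no difference ("there will need to be 4 healthy volunteers per treatment sequence, 16 healthy volunteers total, to have a 95% probability of the measured" ratio in range) and 20 at a 5% difference. The largest of the four, 32, is the number of completers the trial aims for, with at least 36 and at most 40 enrolled.

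The protocol states the Cmax criterion in three ways:

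- Synopsis, Statistical methods: "bioequivalence will be demonstrated if the 90% confidence interval of the ratio of geometric means of AUC" and of Cmax lies within 80% to 125%.
- Section 1.3: the 90% interval is required for AUC. For Cmax, only the relative mean must lie between 80% and 125%.
- Section 12.2: 90% intervals are calculated for Cmax, but the sentence that defines the conclusion says the ratios must lie within 0.80 to 1.25 and names no interval.

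Section 12.3 ends: "The sample size was selected to be consistent with the research hypothesis as described in Section 1.2". Section 1.2 names Cmax, AUC and AUC(0-t) for both drugs but gives no numerical criterion.

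**The concern.** The Cmax statement in Section 12.3 concerns the measured ratio, which is a point estimate. The Synopsis decides Cmax on a confidence interval, which is a much harder test at the same sample size. A sponsor or ethics committee reading Section 12.3 would take 95% as the chance of success on the limiting endpoint. If the Synopsis rule governs, the real chance is clearly lower. The stated 95% also looks wrong for its own criterion, because every volunteer receives both test and reference in each food state and the resulting within-subject variance gives different sample sizes. At stake is the only justification given for N on the endpoint that sets it.

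**Working it through.** **Inputs.** From Section 12.3: intra-subject SD of log Cmax 0.286 (dapagliflozin) and 0.220 (metformin). Limits ±ln 1.25 = ±0.2231. Differences ln 1.00 = 0, ln 1.05 = 0.0488, ln 0.95 = −0.0513 (the protocol gives no direction for its 5% difference). From Section 3.1: four-way crossover, so the test–reference contrast within a food state has SE = SD × √(2/n). N is rounded up to a multiple of 4, one per sequence.

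**Step 1: reproduce the stated Cmax figures.** The criterion is P(−0.2231 < estimate < 0.2231), with the estimate normal around the true log ratio.

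With the doubled variance, SE = SD × √(4/n). For dapagliflozin, n = 32: SE = 0.286 × √(4/32) = 0.1011. At ratio 1.05 the probability is Φ((0.2231 − 0.0488)/0.1011) + Φ((0.2231 + 0.0488)/0.1011) − 1 = Φ(1.72) + Φ(2.69) − 1 = 0.954. All four stated values come out:

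| Drug, ratio | Stated N | Probability at stated N, 4·SD²/n | Probability at N − 4, 4·SD²/n | N needed for 95%, 2·SD²/n |
|---|---|---|---|---|
| Dapagliflozin, 1.00 | 28 | 0.961 | 0.944 | 16 |
| Dapagliflozin, 1.05 | 32 | 0.954 | 0.941 | 16 |
| Metformin, 1.00 | 16 | 0.957 | 0.921 | 8 |
| Metformin, 1.05 | 20 | 0.959 | 0.937 | 12 |

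**Step 2: point-estimate rule with the crossover variance.** For dapagliflozin, n = 32: SE = 0.286 × √(2/32) = 0.0715. At ratio 1.05: Φ(0.1744/0.0715) + Φ(0.2719/0.0715) − 1 = Φ(2.44) + Φ(3.80) − 1 = 0.993. At 0.95 it is 0.992, and at no difference 0.998. With n = 16 the values are 0.973 (ratio 1.00), 0.954 (1.05) and 0.952 (0.95).

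**Step 3: 90% CI rule.** This is two one-sided tests at 5%, with t on 3n − 6 degrees of freedom. At n = 32, df = 90, t = 1.662 and the half-width is about 1.662 × 0.0715 = 0.1188, so the estimate must lie within ±(0.2231 − 0.1188) = ±0.1043. Treating the SD as known:

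- Ratio 1.00: 2Φ(0.1043/0.0715) − 1 = 2Φ(1.46) − 1 ≈ 0.855.
- Ratio 1.05: Φ((0.1043 − 0.0488)/0.0715) + Φ((0.1043 + 0.0488)/0.0715) − 1 = Φ(0.78) + Φ(2.14) − 1 ≈ 0.765.

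Exact power, allowing for an estimated SD:

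| Completers | Ratio 1.00 | Ratio 1.05 | Ratio 0.95 |
|---|---|---|---|
| 32 | 85.4% | 76.4% | 75.5% |
| 36 | 90.0% | 81.3% | 80.4% |
| 40 | 93.2% | 85.2% | 84.3% |

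A simulation of 400,000 draws at n = 32 agrees. With the smaller n − 2 degrees of freedom the first row becomes 84.0%, 75.1% and 74.2%, so that choice matters little. Power of 95% would take 44 completers at no difference and 60 to 64 at a 5% difference. Metformin Cmax at 32 completers has 98% (ratio 1.00) and 93% (a 5% difference), so dapagliflozin Cmax is the limiting endpoint.

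**Step 4: the AUC figures in the same section.** For metformin, where "Using a 90% power and a 2-sided alpha of 5%, there will need to be 5 healthy volunteers per treatment sequence" (20 in total), the stated 20, 24 and 24 reproduce with SD 0.180, variance 2·SD²/n and one-sided 2.5%. At one-sided 5%, which is what a 90% interval implies, they become 16, 20 and 20. For dapagliflozin AUC (SD 0.093), the settings that reproduce the metformin figures give 8, not the stated 12: n = 8 already has 99.0% at no difference and 94.3% at ratio 1.05. No single formula therefore accounts for the whole section.

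**The case against.** The strongest reply is that Section 12.3 was written for the rule in Section 1.3, which asks only that the mean Cmax ratio lie in range, and that the concluding sentence of Section 12.2 can be read the same way. On that reading 32 is more than enough and any error is conservative. This stands in part: the shortfall depends on the Synopsis rule, and a reader might wrongly infer that the trial is simply underpowered. The reply does not rescue the 95%, which is then too low. Nor does it remove the Synopsis rule, which the 90% intervals calculated for Cmax in Section 12.2 make plausible.

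Three further inferences go beyond the documents:

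- **That a doubled variance was definitely used.** The protocol states no formula. Four matches are strong evidence, but the dapagliflozin AUC figures do not fit the formula that reproduces the metformin ones.
- **That success in both food states is only 57–58% (73% at no difference).** This squares the per-state power (0.764² = 0.584; 0.755² = 0.570; 0.854² = 0.729) and so assumes independence between states. The documents give no correlations, and the protocol claims no joint power.
- **That the two-sided alpha of 5% undermines N.** It makes the metformin AUC figures larger, not smaller, and all of them are below 32.

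The reply that more than 32 may complete is also fair. Still, even 40 completers reach 93% at most under the interval rule.

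**Conclusion.** The point holds in this form: the 95% attached to 32 completers is wrong under every Cmax rule that the protocol states. Under the 90% interval rule it should read about 85% at no difference and about 76% at a 5% difference, per food state and for dapagliflozin Cmax alone. Under the point-estimate rule it should read about 99%. These figures rest on the protocol's SD of 0.286, a normal model on the log scale, the crossover variance and 32 completers. The underlying defect is that the Synopsis, Section 1.3 and Section 12.2 do not agree on how Cmax is judged, so Section 12.3 cannot be right until they do. The protocol does not settle which rule governs, and it does not show that N is too small.

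**What to change.** First, choose one Cmax decision rule and state it identically in the Synopsis, Section 1.3 and Section 12.2. Then restate the Cmax probabilities in Section 12.3 for that rule with variance 2·SD²/n, and write the formula down. For dapagliflozin at 32 completers that means about 85% (no difference) and 76% (5% difference) per food state if the 90% interval applies, or about 99% if the point estimate applies. Recalculate the metformin Cmax statements in the same way. Keep 36 enrolled and 32 completers.

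Optionally, replace the two-sided 5% alpha by two one-sided tests at 5%, to match the 90% interval. The metformin AUC sample sizes then become 16, 20 and 20, with no effect on N. A joint power figure is not needed; if one is given, label it as assuming independence.

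The cost is a text change with no extra volunteers. The drawback is that the stated Cmax power may become less favourable, and the sponsor would then have to accept that figure knowingly.
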